Study Protocol Document Cover Page

Official Title of the Study: Trial of Self-managed Approaches for Patellofemoral Pain Syndrome in Active Duty Military

NCT Number: NCT02597673

Date of Document: July 16, 2015

Trial of Self-managed Approaches for Patellofemoral Pain Syndrome in Active Duty

Objective

The overall objective of this project is to compare the three home-managed treatment regimens for PFPS: neuromuscular electrical stimulation (NMES), transcutaneous electrical nerve stimulation (TENS), and NMES combined with TENS to a standard home exercise program (HEP). Each of the three treatment arms will be supplemented by HEP and compared to a group receiving standard HEP alone. Our central hypothesis is that the combination of NMES with TENS will show significantly greater improvements in muscle strength, mobility, pain, daily activity and quality of life (QOL) than HEP alone.

Design

The Study will use a two-by-two factorial (NMES +/- and TENS +/-) design with repeated measures over time to compare the effects of NMES, TENS and combined NMES/ TENS on strength, mobility, symptoms, and QOL on military members with PFPS to the effects of a standard home exercise program. All groups will participate in the standard home exercise protocol. The groups will be assessed over 9 weeks to compare main and interactive effects over time. All groups will have an intensive 9-week program.

Participants will be randomly assigned to 1) NMES with the standard HEP protocol; 2) TENS with standard HEP protocol; 3) NMES and TENS with standard HEP protocol; and 4) standard HEP protocol alone (control group). We will not randomize participants until after the pre-treatment assessment has been completed. Participants will be familiarized with the test procedures prior to baseline testing, and then assessed again at 3, 6 and 9 weeks. The primary outcome measures are lower extremity muscle strength, physical activity, and mobility; and the secondary measures are symptoms/pain and QOL.

Methods

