Three locations (per limb) for the strength measurement will be taken using the MMT. To assess knee extension, the first measurement will be 5 cm distal to TT on the anterior limb. To assess knee flexion, the second measurement will be 5 cm distal to TT on the posterior limb. The third measurement will be the standard protocol for the MMT (distance from the tibial tuberosity to the superior aspect of the medial malleolus, multiplying by 0.6); this measurement will be used as a standard normative reference for strength comparisons to other populations. Each participant's muscle groups will be tested in the following order: right knee extensors (RKE), right knee flexors (RKF), left knee extensors (LKE), left knee flexors (LKF).

For each test, participants will perform three maximal efforts holding each contraction for 4 seconds, separated by 30-second rest; the highest value of the three trials will be accepted in kilograms. Reliability of the NMMT was determined by using 1-day repeat testing with intrarater correlation coefficients ranging from .97 to .99 50. Pearson correlation coefficients between the NMMT and a Cybex II dynamometer ranged from .64 to .76 50.

Assessment of Mobility and Physical Activity: Mobility will be measured by these procedures: a timed stair climb, step down test, timed chair rise test and a 6-minute walk test. Additional physical activity measures will be the monitoring of steps walked and energy expenditure.

The Timed Stair Climb Test will test the functional activity of stair climbing. The test will begin with participants ascending up four steps (6-inch rise, 11.5-inch run) to a 30-inchesquare platform, and then descending to the bottom of the stairs. Participants will climb the stairs at a self-selected pace using the handrails if necessary. Each participant will complete two complete rounds, if possible, and the two times will be averaged to produce one score. Performance-based measures such as the stair climb have high test-retest reliability and are inversely correlated to quadriceps muscle strength and cardiovascular capacity. After completing the test, a visual analog scale (VAS) for pain will be administered to quantify pain during the effort.

The Forward Step-Down Test is a specific function test for PFPS, putting weight bearing stress during a movement that mimics stair descent. The test is performed from a 20 cm (8 inch) high platform.

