The participant steps forward and down toward the floor from a single-leg stance with a straight knee (hands on hips). The knee of the stance leg bends until the opposite foot lightly touches the floor with the heel and then returns to full knee extension. The heel touching the floor is not to be used to accelerate back onto the platform. This counts as one repetition; the number of repetitions performed in 30 seconds is recorded. Both legs are tested separately. The intraclass correlation coefficient for the step-down test reliability was 0.94 with standard error of the mean 0.5354. The correlation coefficient between the step-down test and the VAS for pain was 0.57 ($p<0.01$)⁵⁴.

The 30-Second Chair Stand Test assesses lower-body strength mimicking squatting. The participant completes as many full stands as possible in 30 seconds. The participant sits in the middle of the chair, feet flat on the floor with arms crossed at the wrists and held against the chest. When instructed, the participant rises to a full stand, and then returns to a fully seated position. The number of completed rises will be recorded. The correlation coefficients of chair stand test scores to leg press (1RM) scores was $r=0.68$.

The 6-Minute Walk Test (6-MWT) measures the distance a participant walks at a “fast” pace over a 6-minute period. Participants will “walk as quickly as you can” with the opportunity to stop and rest if required. This test measures functional capacity of walking. Normal reference for healthy adults on the 6-min walk distance has been published. The 6-MWT has demonstrated submaximal exercise at 72.7% \pm 11.6% of $\dot{V}O_{2\text{max}}$. with rank order correlation of 0.49 ($P = 0.001$) between 6-MWT and $\dot{V}O_{2\text{max}}$. Test-retest reliability was $\text{ICC} = 0.917$ [0.862-0.951]).

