Mobility: Physical Activity Measures: Physical activity will be measured using the Fitbit Charge (San Francisco, CA). The Charge is a wrist-worn three-axis accelerometer that measures steps walked, distance traveled, energy expenditure and floors climbed. The frequency, duration, intensity and patterns of movement are recorded. The unique feature of this device is a wireless function that automatically uploads data to designated mobile phone devices or computers. Batteries are rechargeable and last 5-7 days. Fitbit products use similar accelerometry for all their products. Thus, we assume that each of their products have similar validity and reliability. In our personal experience comparing the Charge to the Jawbone and the well validated Digiwalker, we found very similar accuracy of steps. Fitbit devices have been shown to be reliable and valid when compared to standard research-grade devices for energy expenditure ($r=0.89-0.97$). Fitbit accuracy estimates report 10% error (90% CI) for energy expenditure compared to a portable metabolic system. In the current study, baseline data will be ascertained by wearing the Charge for 3 days while maintaining a typical activity pattern. Subsequently, the device will be worn daily for 9 weeks.

Assessment of Symptoms of Patellofemoral Pain Syndrome: Pain associated with activity limitations will be measured by the Kujala Anterior Knee Pain Scale 64, a 13-item knee specific self-report questionnaire. Scores range from 0 to 100 with higher scores indicating better performance. In patients with anterior knee pain, high test-retest reliability was demonstrated over 2-3 days ($\text{ICC}=0.95$), with moderate change score correlations ($r=0.42$).

Knee Injury and disability will be measured by the International Knee Documentation Committee (IKDC) subjective knee form, a well standardized outcomes questionnaire that is knee-specific and assesses patients with various knee disorders⁶⁶. The 18-item instrument assesses symptoms, function and level of sports participation for those with an injured knee. The IKDC subjective knee form has demonstrated reliability, construct and concurrent validity and responsiveness.

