Statistical Analysis Plan Document Cover Page

Official Title of the Study: Trial of Self-managed Approaches for Patellofemoral Pain Syndrome in Active Duty Military

NCT Number: NCT02597673

Date of Document: July 16, 2015

Trial of Self-managed Approaches for Patellofemoral Pain Syndrome (PFPS) in Active Duty Military

Statistical Analysis Plan for PFPS Study

Data Analysis: The primary goal of the analysis is to compare changes over time in the three treatment groups and a usual care control group.

Statistical Assumptions will be examined. For these analyses we will use simple measures of central tendency (means, medians, and mode) and variability (standard deviations). Means and standard deviations will be calculated for continuous variables and percentiles for categorical variables. Baseline Group Differences. ANOVA and Fisher Exact Test will be used to test for differences in baseline characteristics by groups and groups will be compared for equivalence of potentially confounding variables (such as age, rank and gender). Group inequities will be controlled in the analyses by using covariates or other appropriate statistical methods. Time Differences. Linear mixed effects regression models will be used to examine differences in time trends for the outcome variables among controls and those in the treatment groups. Random effects for subject will be included, and time will be examined. Our previous experience has been that for this type of intervention we find little variance explained by a random effect for time. The primary determination of group by time differences will use time as a continuous variable. In these regression analyses, the important primary measures will be expressed as a function of time, treatment group, and group-by-time interactions, while controlling for important covariates. Secondary analyses will include time as a factor to examine responses at individual time points.

Specific Aim I: To determine whether the treatment regimens are significantly more efficacious than standard HEP, using linear mixed effects models, as described above, we will estimate separate models for each of the following dependent variables: knee strength for flexion and extension, energy expenditure, time to complete a step down test, steps walked per day, distanced walked in 6 minutes, and number of times to complete the chair rise.

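### Aim I tests seven unranked primary-domain variables in separate models with no alpha, success rule or error control, and the SAP does not carry forward the protocol's central contrast

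*SAP*

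**What the plan says.** The protocol (Design) sets primary status by domain, not by variable: "The primary outcome measures are lower extremity muscle strength, physical activity, and mobility". The SAP (Specific Aim I) asks whether the regimens beat standard HEP significantly, and "we will estimate separate models for each of the following dependent variables: knee strength for flexion and extension, energy expenditure". The rest of its list is the step-down test, daily steps, 6-minute walk distance and chair rises.

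Three framings of the group comparison stand side by side:
- **Central hypothesis** (Protocol, Objective): against HEP alone, the "combination of NMES with TENS will show significantly greater improvements in muscle strength, mobility, pain, daily activity and quality of life".
- **Factorial** (Protocol, Design): "The groups will be assessed over 9 weeks to compare main and interactive effects over time".
- **Three treatment groups and a control** (SAP, Data Analysis). The SAP mentions neither factorial main effects nor the central contrast.

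The SAP does fix the form of the test. The group-by-time comparison with continuous time is primary, and time as a factor is secondary.

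The two documents also differ on the variables:
- **Stair climb.** The protocol says "Mobility will be measured by these procedures: a timed stair climb, step down test, timed chair rise test and a 6-minute walk test". Aim I omits the stair climb.
- **Step-down.** In the protocol "the number of repetitions performed in 30 seconds is recorded". In the SAP the variable is "time to complete a step down test".
- **Limb.** Strength and step-down are measured on both legs. The protocol defines an index knee for bilateral disease (note after the exclusion criteria), but the SAP does not say which limb is analysed.

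**The concern.** The plan promises a verdict on significance but does not say what would produce it. Seven models give seven group-by-time results, and more if several group contrasts are read from each. With no alpha and no rule for combining the results, the choice between any one variable, a particular variable and all variables stays open until the results are known. If one nominally significant variable were taken as enough, the chance of a false efficacy claim would be well above the level that a reader would assume.

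The mixed model does not address this. It handles repeated measures within one outcome, not error across seven separate outcomes. Nor can an adjustment be specified while the membership and definition of the variables differ between the documents.

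**Working it through.** **Inputs from the documents.** Aim I has 2 strength variables (flexion, extension), energy expenditure, step-down, steps per day, 6-minute walk and chair rise: 2 + 5 = 7. The sample is 136, or 34 per group (Protocol, Study population), and 4 × 34 = 136. That is the only design figure that can be checked. The documents give no alpha, power, effect size, SD, dropout or error rate, so there is no stated error rate to reproduce.

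**Assumptions.** Two-sided 0.05 per test, no true effects, and exchangeable normal test statistics with correlation ρ from 0 to 0.9. Zero correlation is the upper bound here and is unlikely to hold exactly, because steps and energy expenditure come from one "wrist-worn three-axis accelerometer that measures steps walked, distance traveled, energy expenditure and floors climbed".

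**One contrast (NMES+TENS versus HEP), seven variables.** At ρ = 0:
- at least one false rejection: 1 − 0.95^7 = 0.302;
- at least one false claim of benefit: 1 − 0.975^7 = 0.162.

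For ρ > 0, write each statistic as Z_j = √ρ·U + √(1−ρ)·e_j, with U and e_j independent standard normal. Let a(U) = (1.96 − √ρ·U)/√(1−ρ) and b(U) = (−1.96 − √ρ·U)/√(1−ρ). Averaging over U by numerical integration:
- any false rejection = 1 − E{[Φ(a) − Φ(b)]^7};
- any false benefit = 1 − E{Φ(a)^7};
- all seven falsely beneficial = E{[1 − Φ(a)]^7}.

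| ρ | Any of 7, either direction | Any of 7, benefit | All 7, benefit |
|---|---|---|---|
| 0 | 30% | 16% | below 0.001% |
| 0.3 | 27% | 14% | about 0.001% |
| 0.5 | 23% | 11% | 0.02% |
| 0.7 | 18% | 9% | 0.13% |
| 0.8 | 15% | 7% | 0.30% |
| 0.9 | 11% | 6% | 0.68% |

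A single named variable gives 5% in either direction and 2.5% for benefit. With the stair climb as an eighth variable, the either-direction rate at ρ = 0 is 1 − 0.95^8 = 0.337, and 0.250 at ρ = 0.5.

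**A joint group test instead.** One 3-df group-by-time test per model, with any of seven sufficing, gives 30.2, 27.5, 23.7 and 18.7% at ρ = 0, 0.3, 0.5 and 0.7 (simulation, 400,000 draws). Replacing the single contrast with an overall group test therefore does not remove the problem.

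**Power cost of control.** This assumes 34 per arm, no dropout, and a two-sample comparison of standardised change (noncentral t, 66 df). The first Holm step for seven variables is 0.05/7 = 0.0071.

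| Level | Effect detectable with 80% power | Power at 0.69 SD |
|---|---|---|
| 0.05 | 0.69 SD | 80% |
| 0.05/7 | 0.88 SD | 53% |
| 0.05/8 | 0.89 SD | 51% |

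**The case against.** The strongest reply is that the inflation depends on a rule that the plan never states. The central hypothesis joins its domains with an and. Read literally, support requires every domain, and a rule that requires all variables does not inflate error. This stands: no error rate for the trial has been shown, only the rate under one rule that the text leaves open. But the SAP does not adopt the conjunctive reading either, and running seven separate tests as written lets one nominally significant result be offered as efficacy.

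Three stronger readings are tempting, and the documents do not support them:
- A reader might infer that no contrast is named at all. The protocol's Objective does name one, NMES+TENS against HEP alone. The gap is that the SAP does not carry it forward, and two other framings compete with it.
- A reader might infer a false-positive chance of about 60% or more. Seven variables for each of three arms against a shared control give 61% at ρ = 0, and seven for each of two main effects and an interaction give 66%. Both require any one of 21 tests to count, which fits poorly with a single central hypothesis, and the SAP mentions no main effects.
- A reader might infer that pain and QOL need to be relabelled. The protocol (Design; Outcome Measures) already makes them secondary.

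It is also fair to say that the confirmatory contrast is the sponsor's choice. Aim I speaks of regimens in the plural, the design is declared factorial, and a gatekept joint test would be equally valid.

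**Conclusion.** The point holds in this form: seven unranked variables from the primary domains, separate models, no alpha, no success rule, no error control, and a central contrast that does not reach the SAP. The established defect is an undefined decision rule.

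The size is conditional. Under an any-one rule, the single central contrast carries a two-sided false-positive chance between 30% (uncorrelated) and 11% (correlation 0.9). It is above 5% at every correlation tried. These figures rest on an assumed 0.05 per test and an assumed exchangeable correlation. An all-variables rule or one named variable would leave error uninflated.

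**What to change.** Amend the SAP before group results are seen.

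1. **Reconcile the Aim I list with the protocol.** State whether the timed stair climb is in or out, whether the step-down is a count or a time, and that the index knee is the limb analysed for strength and step-down.
2. **State a two-sided familywise alpha of 0.05 and name the confirmatory contrast** as a continuous-time group-by-time comparison. NMES+TENS versus HEP alone is the natural choice, being the stated central hypothesis. The sponsor may prefer another contrast or a gatekept joint test. Label the remaining contrasts secondary.
3. **Adopt one success rule:**
   - one named primary variable, with the others secondary; or
   - Holm across the reconciled variables, with claims limited to those rejected; or
   - an explicit requirement that all variables succeed, which needs no adjustment.

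Aim II needs no relabelling. The SAP should say that success on Aim I alone does not confirm the pain and QOL parts of the hypothesis.

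**Cost.** SAP wording only, with no change to participants or data collection. A named variable loses no power. Holm has the first-step cost tabulated above, but if all seven variables truly differ by 0.69 SD, the chance of at least one Holm rejection is over 99, 95, 90 and 82% at correlations 0, 0.3, 0.5 and 0.7 (simulated). In the same scenario an all-variables rule at 0.05 each has only 21% (0.80^7 = 0.21), 36, 45 and 54% power, so the sponsor should choose it knowingly.

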Specific Aim II: To determine whether the treatments improve QOL and symptoms of PFPS significantly more than HEP, using the same mixed effects method as with Specific Aim 1, we will estimate separate equations for PFPS pain symptom dependent variables. Primary independent variables will be treatment group, time, and group-by-time interaction.

Missing Data. Missing data rates and patterns will be assessed; in particular, missing data rates by treatment group will be examined. For the primary analysis, we will adjust for missing data by using an intent-to-treat analysis. All of the subjects in the study will be included in the analysis. Treatment effects will be compared on the basis of the subject's original group assignment. In addition to the traditional intention-to-treat analyses, we will assess patterns of change both within and between groups using the mixed effects regression models.

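### Does the lack of a wear rule for the activity tracker let unworn days count as inactivity in the step and energy outcomes?

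*SAP*

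**What the plan says.** The Protocol (Design) names physical activity among the primary outcomes. Under Physical Activity Measures, "baseline data will be ascertained by wearing the Charge for 3 days while maintaining a typical activity pattern", and then "Subsequently, the device will be worn daily for 9 weeks". On power supply it says "Batteries are rechargeable and last 5-7 days".

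The SAP (Specific Aim I) fits a separate mixed model to each outcome in a list that includes "energy expenditure, time to complete a step down test, steps walked per day". Under Time Differences the primary test is settled: "The primary determination of group by time differences will use time as a continuous variable". The factor version of time is supportive: "Secondary analyses will include time as a factor to examine responses at individual time points".

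On missing data the SAP says "For the primary analysis, we will adjust for missing data by using an intent-to-treat analysis" and adds "All of the subjects in the study will be included in the analysis", with comparison by assigned arm. The same paragraph opens with a plan to examine how much is missing, and in what pattern, in each arm. It closes by naming the mixed models again.

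Neither document gives a wear threshold, a minimum number of valid days, or the days that form the baseline and week 3, 6 and 9 values. The Protocol's adherence section covers exercise and stimulation sessions, not tracker wear.

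**The concern.** Intent-to-treat acts on participants, whereas tracker data go missing by the day. A participant can attend every visit and still have many unworn days. If an unworn day is stored as few or no steps, it does not look missing. The mixed model would take it as a real low value, and a tabulation of missing rates by arm might not reveal it.

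The design also seems to load the problem onto follow-up. Three baseline days fit within one battery charge, and nine weeks need many charges. Non-wear that grows with time would feed straight into the group-by-time slope, which is the primary test. If it grew faster in one arm, part of the apparent treatment effect would be a wear effect. If it grew equally, a true difference would shrink and person-to-person noise would rise. Either way, a primary outcome could turn on a choice left open until the data are seen.

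**Working it through.** **Inputs from the documents.** 34 per group in 4 groups: 4 × 34 = 136. Follow-up wear: 9 × 7 = 63 days per person, so 136 × 63 = 8,568 person-days. Charges over follow-up: 63/7 = 9 to 63/5 = 12.6. The documents give no non-wear rate, no SD for steps, and no statement of how the device records unworn time. The plan therefore has no figure to reproduce, and everything below rests on assumptions.

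**One unworn day counted as zero.** It lowers a 7-day mean by 1/7 = 14.3% and the 3-day baseline mean by 1/3 = 33.3%. If the unworn shares are p₁ and p₂ and true mean steps are μ in both arms, the observed means are μ(1 − p₁) and μ(1 − p₂). The false difference is μ(p₁ − p₂). For 20% against 10% it is 0.10μ.

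**Single comparison of two arms.** In SD units, d = 0.10/CV and SE = √(2/34) = 0.243. The false-positive rate is Φ(d/SE − 1.96) + Φ(−d/SE − 1.96).

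| Assumed CV | d | False-positive rate |
|---|---|---|
| 0.3 | 0.33 | 28% |
| 0.4 | 0.25 | 18% |
| 0.5 | 0.20 | 13% |

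**Group-by-time slope, no true effect, non-wear rising linearly to the week-9 shares shown.**
- Simulation A: random-intercept model, 7-day windows, person and day CV 0.3 to 0.4, within-person correlation 0.5 to 0.8, non-wear varying between persons (Beta, concentration 5), 2,000 runs per setting.
- Simulation B: per-person slopes, 21-day windows, person CV 0.4 with each person's level constant over time, day SD 0.3 of the mean, 4,000 runs per setting.

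| Simulation | Unworn at week 9 | Zeros kept | Set to missing |
|---|---|---|---|
| A | none | 6.2–6.5% | same analysis |
| A | 15% v 10% | 9–14% | 6% |
| A | 20% v 10% | 21–35% | 7–8% |
| B | 20% v 20% | 5% | 4% |
| B | 20% v 10% | 54% | 5% |
| B | 30% v 10% | 98% | 5% |

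An independent repeat of A's settings gave 10–13% for 15% v 10% and 17–30% for 20% v 10%. A slope t-test in two of A's settings gave 19–21% for 20% v 10%, and 5–6% for a gap of 12% v 10%, which is no visible inflation.

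**Power with equal non-wear (A, correlation 0.5 to 0.7).** Full wear gives 74–76%. At 10% in both arms, power is 53–62% with zeros kept and 70–73% with unworn days set to missing. At 20% in both arms it is 42–53% and 66–72%. The loss depends on how non-wear is spread over people. In the slope t-test, equal 10% non-wear took power from 79–80% to 62–66% with the same Beta spread, but only to 69% when everyone had the same rate.

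**Clinic-visit outcomes.** With 20% dropout driven by pain in one arm only, and a pain–outcome correlation of 0.57 (the Protocol's figure for the step-down test against VAS pain), the mixed-model week-9 contrast shifts by 0.02 to 0.07 SD. The concern does not extend to these outcomes.

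**What the harm needs, set against the text.**
1. *Unworn days stored as low values.* The Protocol does not say this. A tracker with an empty battery may leave no record, which would be ordinary missing data.
2. *Those values kept in the analysis.* No passage says so.
3. *Wear that differs by arm, for bias.* All arms have 62 sessions, 4 visits and weekly contact, and contact for the exercise-only group is described as an attention control. The stimulation arms log a stimulator setting, but exercise adherence also comes from participant logs. Handling a thigh or knee stimulator is not evidence about wearing a wrist device.

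**The case for a change.** The best case for a change is that the omission is real, concerns a primary outcome and is cheap to repair: one paragraph and one derivation step. The mixed model cannot correct a zero that it takes as observed, and the by-arm missing-data check is descriptive and does not define missing for tracker data. Fixing the rule before outcomes are seen by arm would remove a choice that could sway the result. If wear proved perfect, the rule would cost nothing.

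Most of this is right as a description. The sentence on intent-to-treat does not reach days, and neither document supplies a rule that does. What does not stand is the step from silence to harm. The plan contains no instruction to count unworn days. A statistician turning raw tracker output into a daily step value has to decide which days carry data, and would normally screen out empty ones. Automatic upload and weekly contact in every arm also give staff the chance to notice gaps.

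Nor is a written rule as simple as it sounds. The Protocol lists features of movement as recorded, not hours of wear. A rule that infers wear from movement can discard truly inactive days, whereas the simulations assume that unworn days are recognised perfectly. Any threshold would itself be a judgement that the documents do not inform. Energy expenditure was not simulated, so the step figures cannot be carried over to it.

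**Conclusion.** No change to the plan. The documents leave the tracker's valid days and analysis windows unstated, and intent-to-treat does not fill that gap. It is a derivation detail that competent analysts would handle sensibly, not a stated rule that produces a wrong answer.

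The possible distortion is not trivial: for 20% v 10% unworn, about 10% of mean steps and a false-positive rate of 13% to 54%. It arises only if unworn days are stored as zeros, kept, and unequal between arms. With equal non-wear the false-positive rate stays near 5%, and the cost is power. With unworn days set to missing, false-positive rates were 4% to 8% in every scenario run. The non-wear rates, variances and storage of unworn time are all assumed, so no size can be fixed from the documents. The figures apply to steps only.
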